1.3 Potential Risks

The research protocol calls for non-treatment seeking smokers, who will vary across the motivational spectrum from wanting to quit vs. not wanting to quit, to receive standard care (Ask, Advise, Refer) or NRT sampling. The sampling intervention consists of a two-week supply of both nicotine patch and lozenge, both over-the-counter products that have received extensive support for their efficacy and safety (19, 97-102). Nonetheless, there are potential for risks for each product alone, as well as when used concurrently. We believe these risks, described below, will be minimal and mild.

1.3.1 Nicotine lozenge In a prior trial of the particular lozenge we will be using, 68% and 71% of 2 and 4 mg users of nicotine lozenge reported an adverse event (AE) vs. 54% of placebo users (103, 104). With both active doses of the lozenge, 7% dropped out due to AEs and 7% dropped out due to AEs on placebo. With both active doses, 1.6% reported a serious AE which was not different than that for placebo. There were no deaths or irreversible injuries deemed possibly due to lozenge. The most common AEs were nausea, flatulence and upper respiratory tract infection (103). The current labeling on OTC lozenge states pregnant and breast feeding women, those less than 18 years of age, those using a prescription medication for depression or asthma or a smoking cessation medication and those with heart disease, recent heart attack, irregular heartbeat, high blood pressure not controlled by medication, stomach ulcers or diabetes should consult a provider before using the lozenge.

In a recent trial of placebo vs. single vs. multiple medications for smoking cessation (85), the three most common adverse events within the lozenge group were 1) nausea: 7.8%, compared to 4.4% within placebo group, 2) mouth/throat irritation: 6.7%, compared to 3.3% within placebo group, and 3) hiccups: 6.2%, compared to 0.3% within placebo group. All other adverse events occurred <5%. In our recent trial of sampling nicotine lozenge, which was not placebo-controlled but was based on a similar sampling strategy as proposed here, the most common adverse events were nausea (23% of all adverse events), throat irritation (17%), and hiccups (13%).

Dependence on the lozenge and harm from concurrent use of lozenge and cigarettes has not been reported but has not been studied. The pharmacokinetics of the lozenge most closely matches that of nicotine gum. With gum used for abrupt cessation, the estimated incidence of dependence is 1-3% (105). Although an early anecdotal report suggested concomitant use of NRT and smoking could induce heart attacks, several large empirical studies since then have failed to confirm this observation (106). For example, in the LHS study (107) and in our prior study (45), large numbers of smokers concurrently smoked and used nicotine gum or other NRT products and the incidence of any significant AEs was < 1%.

1.3.2 Nicotine patch The most common side effects from nicotine patch are skin irritation, insomnia, and headache or nausea. In an early but seminal placebo controlled test of patch (108), there were few systemic side effects of patch use: 21% vs. 15% of smokers in the patch and placebo groups respectively reported a side effect during the treatment period. The most frequent symptoms with the patch as compared with the placebo patch were headache (4 vs. 4 percent), nausea (4 vs. 1 percent), and vertigo (4 vs. 0 percent). Transient mild itching was reported by 14% of the subjects in the patch group and 1% in those in the placebo group after the first week ($P<0.001$). At each visit, 4.5% to 7.3% of the remaining subjects in the patch group reported erythema, as compared with 2.3% to 6.7% of those in the placebo group. Acute eczema persisting for several days in the area of the patch caused 1.4% of the subjects in the nicotine group and 0.7% of those in the placebo group to stop using the patch.

In a separate but similar study comparing bupropion vs. patch vs. combined bupropion/patch vs. placebo (109), the most common adverse events reported by patch participants were 1) insomnia (30% in active patch group vs. 20% in placebo), 2) headache (28% in active patch group vs. 33% in placebo), 3) application site reactions (19% in active patch group vs. 7% in placebo), and 4) dream abnormalities (18% in active patch group vs. 3% in placebo).

1.3.5 Undermining Cessation Another potential risk is that the sampling intervention will decrease rather than increase future cessation as briefly discussed in Section A.5. However, the limited data available (114) suggest this is unlikely. Our prior work on providing NRT to smokers not yet fully committed to cessation (44, 45, 64), as well the work of many others (115, 116) clearly demonstrate that use of pharmacotherapy among smokers not wanting to quit effectively promotes cessation.

1.3.6 Confidentiality A final risk is breach of confidentiality.

2. Adequacy of Protection Against Risks

All recruiting personnel and treatment-delivering providers have or will have up to date CITI Certification for Protection of Human Subjects prior to study initiation.

2.2 Protection Against Risk

2.2.1 Nicotine lozenge The primary protection against risk of the nicotine lozenge (an OTC product) is the short duration for which it will be provided— only a 2-week supply. However, because this is a clinical trial, we will have a Safety and Data Monitoring Plan that includes monitoring of Adverse Events (AEs). An added precaution is the actual delivery of the lozenge, provided directly the participant's primary care provider. We will exclude individuals based on standard FDA contraindications for NRT use (pregnancy, recent cardio trauma). We will clearly advise against use of NRT during pregnancy and breast-feeding but we will not require pregnancy tests to be in the study. Through brochures delivered as part of the sampling intervention, participants will be educated about lozenge AEs and nicotine intoxication symptoms. A physician will be on call throughout the study for questions about AEs, etc. Participants will be encouraged to contact the Study PI as soon as possible for serious AEs and for those conditions that OTC labeling suggests seeing a provider. We will withdraw participants who have a serious AE. For other AEs, if the study physician, the participant's physician or the participant wishes it, the participant will be withdrawn from the study. We will also form a Data Safety and Monitoring Board. If the percent of serious or severe AEs appears to be greater than 5% this board will be notified to make a decision on early termination of the study.

2.2.2 Nicotine patch The same precautions as above apply to the use of nicotine patch.

2.2.3 Combined patch & gum We will not explicitly encourage or discourage use of combined medication. The sampling experience is meant to provide smokers with a real-world opportunity to "test drive" different medications. Our accompanying brochures will discuss the anticipated negative consequences of dual use

(nausea, headache) and advise participants to discontinue one or both products should they arise. Given the 2 week sampling experience, we expect adverse events to be rare and mild.

2.2.4 Combined use of any NRT product and smoking As above, accompanying brochures will advise smokers not to smoke while using NRT product (even though most studies have demonstrated no significant events for combined use (63).

2.2.5 Undermining Cessation To protect against this outcome, we will form a Data Safety and Monitoring Board (DSMB) and have them conduct an interim analysis after 50% of the sample has completed 6 month follow-up. We chose this number as this is the minimum necessary given our base rate is projected to be 15% and one has to see clear trend toward an even lower rate. To do this, the statistician will provide a copy of the dataset to the board. If this occurs, this board will independently decide on whether to stop the study.

2.2.6 Confidentiality We will use the participant's name only on the screening and informed consent documents and these will be kept in a locked file, to be kept centrally at our study office. The research materials will become part of the modern record keeping facility of the Institute of Psychiatry, which will minimize risks to the privacy of participants. All interviews, records, charts, rating scales, and other patient information will be kept on a secure server or in locked files at the Cancer Control Program, with limited access to the study personnel. All database files will be on a secure server or MUSC network drive only accessible to our research group and include password protection to further ensure confidentiality.

3. Potential Benefits of the Proposed Research to the Participants and Others / Importance of the Knowledge to be Gained

All smokers in this trial will receive at minimum standard care, consisting of brief provider advice to quit and referral to quitting resources. Half of the participants in the trial will receive samples of two products that alone and in combination have shown significant benefits on quitting. Thus, there are direct benefits to all participants. The major benefit to society will be whether a brief samples of evidence-based medication serve as an effective method to catalyze cessation (abstinence, quit attempts, uptake of additional quit resources). The risks of nicotine lozenge and patch are very small, even when used concurrently. The sampling period of our trial consists of two weeks, which further minimizes risk potential. Smoking cessation is the most important activity to improve public health and many smokers are resistant to quitting. Recent trends in smoking cessation are moving towards longer, more intensive treatments that combine behavioral and pharmacologic treatment. While efficacious, such approaches do not lend themselves to clinical practice within primary care settings, where providers have limited resources (time and expertise) to address tobacco dependence. If NRT sampling results in the hypothesized outcomes, it could offer an innovative, easy to implement option that has significant reach. Thus, NRT sampling represents a significant strategy that offers both clinical and policy significance to promote public health.

4. Data and Safety Monitoring Plan

This section is based on the recommendations in NCI's "Guidelines for Developing a Data and Safety Monitoring Plan" (<http://www.cancer.gov/clinicaltrials/patientsafety/dsm-guidelines/page1>) as well as NIDA's "Guidelines for Developing a Data and Safety Monitoring Plan" (www.drugabuse.gov/funding/dsmb.html).

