4.9 Data Analysis Plan

All analyses are based on an intent-to-treat approach, and are nearly identical to analyses from our current and prior studies. Exploratory analysis will be performed on all variables to determine if transformations are needed. Any significant baseline differences between groups will be included in regression analyses described below. All analyses below will be run separately for full intent-to-treat sample (immediately below), per protocol, and, within the NRT group, using those participants who used single vs. combined NRT products.

Examination of Potential Site Differences Outcomes and patient characteristics will be estimated across clinics using summary statistics and confidence intervals. This will be considered an exploratory analysis due to the relatively large number of clinics and, hence, the large number of multiple comparisons that could arise. Grouped logistic regression modeling may be used to describe associations between clinic characteristics and binary clinical outcomes (e.g., quit rate).

Missing Data & Dropout The most conservative approach for handling missing data is to substitute them with baseline values, assuming outcomes have all returned to baseline, with no quit attempts made or abstinence achieved. If this assumption is incorrect, it biases the results towards the null by reducing between group differences. Since we expect few missing data, we will use this approach. If missing data >10%, we will calculate results using this conservative method but also using methods in which missing data are imputed as described in the SRNT guidelines. We will also assess whether dropout is differential by study group. In our current and recent studies of cessation induction, this has not been the case. Abstinence will be reported both with and without (missing samples) cotinine verification.

Hypotheses 1a, 2, & 3 These hypotheses predict that provision of NRT samples will lead to higher abstinence rates (Hyp. 1a), incidence of quit attempts (Hyp. 2), and uptake of additional treatment (Hyp. 3). Logistic regressions will be performed for each outcome with treatment group (standard care vs. NRT sampling)

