4.11 Reporting mechanisms of AEs/SAEs to IRB, FDA, NIDA

Prior to the start of the study, the protocol will be registered on the clinicaltrials.gov registry. In our prior work on smoking reduction, in which smokers were using OTC NRT for non-cessation indications, we three times filed for an IND with FDA. On all three occasions the FDA has stated an IND is not necessary. For this study, we do not believe an IND is necessary, but we will again notify FDA of our intent to conduct a trial with a non-approved indication.

Serious Adverse Events (SAEs) are defined as any even that is fatal or life threatening, is permanently or significantly disabling (physically or psychologically), requires inpatient hospitalization or prolongation of hospitalization, contributes to a congenital anomaly/birth defect or is any medical event that requires treatment to prevent one of the medical outcomes listed above.

For a study of this size (N=1300) and duration (6 months), we do expect some deaths to naturally occur, all of which will be reported to IRB, but given that we are providing a mere 2-week sample of NRT, we do not anticipate any study-related SAEs. In our ongoing trial of now 1200 smokers followed for 1 year, there have been <5 deaths total.

All serious AEs (SAEs), study related or not, will be reported to the MUSC Committee on Human Research within 72 hrs. We will also report SAEs to NIDA within 72hrs of learning of any such occurrence, using the NIDA SAE Report Form. Follow-up of all unexpected and serious AEs will also be reported. All AEs are reviewed weekly by the PI and yearly by the IRB. Any significant actions taken by the local IRB, protocol changes will be relayed to the funding agency. We estimate the significant AE rate to be 5% or less. If the monthly monitoring indicates the rate is above this, we will convene a special meeting of the DSMB.

4.12 Reporting mechanisms of IRB actions to NIDA & Report of changes or amendments to the protocol

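### A serious AE appears to end study follow-up, so a participant hospitalised for an unrelated reason would be scored as not abstinent at 6 months

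*Combined protocol and SAP*

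**What the plan says.** Section 2.2.1 (nicotine lozenge) states: "We will withdraw participants who have a serious AE". The sentence does not say what the participant is withdrawn from, but the one after it does: "For other AEs, if the study physician, the participant's physician or the participant wishes it, the participant will be withdrawn from the study". Section 2.2.2 carries the rule over: "The same precautions as above apply to the use of nicotine patch".

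The definition of a serious AE in 4.11 includes any event that "requires inpatient hospitalization or prolongation of hospitalization". It is not limited to related events or to the sampling period. The same section expects no SAEs related to the study, and it adds: "Follow-up of all unexpected and serious AEs will also be reported".

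Section 4.1 schedules assessments at 1, 3 and 6 months and makes 7-day point prevalence abstinence at 6 months the primary outcome.

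Section 4.9 states: "All analyses are based on an intent-to-treat approach". Missing outcomes take their baseline values, "assuming outcomes have all returned to baseline, with no quit attempts made or abstinence achieved". Imputation is added only if more than 10% of data are missing. The section also undertakes to check whether dropout differs by group.

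**The concern.** The rule would create missing primary outcomes in people who could still be telephoned. Product is a two-week supply, and standard-care participants receive none. For most of the 6 months there is no study product left to stop, so all that withdrawal can end is follow-up. Because the plan expects no related SAEs, the rule would act almost entirely on unrelated events. A participant who had quit and was then hospitalised in month 4 would be counted as smoking at month 6.

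Two things are at stake. If withdrawal is equally common in both arms, the treatment contrast is diluted. If it is more common in the sampling arm, the comparison is biased against NRT, and the loss would resemble the undermining of cessation that the DSMB is asked to watch for (2.2.5, 4.13a). The second possibility is open because the rule appears only under the lozenge and patch headings, no blinding is described, and the brochures describing AE symptoms belong to the sampling intervention.

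**Working it through.** **Inputs from the documents.** N = 1,300 (4.4), taken as 650 per arm because half the sample receives NRT. Base abstinence rate 15% (2.2.5, 4.13a). One-sided 0.025 test (4.9). Power 0.80 before the interim look (4.13b, 4.17).

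**Assumptions.** The documents project no SAE rate. Section 4.11 puts significant AEs at 5% or less. That is not an SAE rate, but it serves as an upper planning value, so the share withdrawn, s, is taken as 1% to 5%. The sampling-arm rate and intraclass correlation are not in the documents available (4.4 points to a grant section), so N = 1,300 cannot be reproduced. Instead, the sampling-arm rate is solved to give power 0.80 with 650 per arm. Without clustering it is 20.96%, a difference of 5.96 points.

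**Numbers affected.**
- Both arms covered: 1,300 × 0.01 = 13, and 1,300 × 0.05 = 65.
- Sampling arm only: 650 × 0.01 = 6.5, and 650 × 0.05 = 32.5.
- Only would-be abstainers are misclassified. In control, 650 × s × 0.15 gives 1.0 to 4.9. In the sampling arm, 650 × s × 0.2096 gives 1.4 to 6.8.

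**Effect on power.** Scoring a share s as smoking multiplies that arm's abstinence rate by (1 − s). Power = Φ[(d − 1.96 × SE0) / SE1], where d is the difference in rates, SE0 is the pooled standard error and SE1 the unpooled one.

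Example, both arms at s = 5%: the rates are 14.25% and 19.91%, d = 0.0596 × 0.95 = 0.0566, SE0 = 0.0209 and SE1 = 0.0208, and power is 0.775.

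| s | Difference, both arms | Power, both arms | Difference, sampling arm only | Power, sampling arm only |
|---|---|---|---|---|
| 0 | 5.96 points | 0.800 | 5.96 points | 0.800 |
| 1% | 5.90 | 0.795 | 5.75 | 0.773 |
| 2% | 5.84 | 0.790 | 5.54 | 0.744 |
| 5% | 5.66 | 0.775 | 4.91 | 0.646 |

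At s = 5% in both arms, the total N needed for 0.80 power rises from 1,300 to about 1,384.

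**Clustering.** With design effects of 1.64 and 2.28 (assumed intraclass correlations of 0.01 and 0.02, 65 per clinic) and the sampling-arm rate solved again, the both-arms column is almost unchanged (0.775 and 0.774 at 5%). In the one-arm case, power across the three design effects is 0.773 to 0.781 at 1% and 0.646 to 0.692 at 5%.

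**Bias with no true effect, sampling arm only.** −0.15 × s gives −0.15 to −0.75 percentage points.

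**Would the existing sensitivity analysis catch it?** At 5% or below, these withdrawals would not by themselves reach the 10% trigger for imputation.

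**The case against.** The strongest counter-argument is that the key link is inferred. No section says that outcome calls stop after withdrawal, and the serious-AE sentence sits among product precautions, so the sponsor may have meant product only. The inference nevertheless remains the plain reading. The following sentence opens with other AEs and speaks of leaving the study, and no section keeps these participants in follow-up. If product only was meant, the same clarification is needed.

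A reader might draw stronger conclusions that the documents do not support:

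- **That every outcome is lost.** Quit attempts, abstinence duration and treatment uptake already reported at 1 or 3 months are observed, and nothing says they are discarded. What is wholly lost is the 6-month abstinence status and anything that would have been reported later.
- **That the rule contradicts intent-to-treat.** Keeping everyone and scoring missing as smoking is one form of intent-to-treat analysis.
- **That it contradicts 4.11.** That section is about reporting the course of events, not about abstinence calls.
- **That safety observation ends.** Unexpected AEs are monitored while active (4.13c, 4.16), the follow-up of serious AEs is reported (4.11), and consent allows medical-record access for up to two years (1.2).

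It also stands that 4.9 acknowledges bias towards the null from missing data and plans a check for differential dropout. That check can reveal an imbalance but cannot recover outcomes that were never collected.

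**Conclusion.** The concern holds at moderate severity. As written, the plan gives up primary outcomes in participants who may still be reachable and scores them as not abstinent. With equal withdrawal of 1% to 5%, the cost is about 0.5 to 2.5 points of power. At 2% it equals the loss the plan already accepts for its interim look (0.80 to 0.79).

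A reader might infer a large bias from the one-arm figures, a loss of roughly 2 to 15 points of power. Those figures require the rule to act only in the sampling arm. The text leaves that open and does not establish it.

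The conclusion rests on withdrawal ending the remaining assessments and on the assumed SAE range. The counts are upper values for a given rate. They treat every SAE as falling before the 6-month contact and every affected participant as otherwise reachable, although deaths would be missing in any case.

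**What to change.** In 2.2.1 and 2.2.2, separate stopping study product from leaving follow-up. State that, in both arms, the 1, 3 and 6 month assessments continue after a serious or other AE unless the participant withdraws consent to follow-up. In 4.9, add that outcomes observed after such an event are used in the intent-to-treat analysis. Reconcile 2.2.1, 4.9 and 4.11 so that withdrawal has one meaning throughout. Whether and when product is stopped stays with the sponsor and is not touched by this change.

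The cost is a sentence in 2.2.1/2.2.2 and a matching line in 4.9. The assessments are already scheduled. The small downside is a few more calls to participants who have been ill.

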4.1 Summary of the Protocol

The design calls for a 2-group, randomized clinical trial of 1) standard care (Ask, Advise, Refer) vs. 2) standard care + NRT sampling. Randomization will be at the clinic level, but the unit of analysis is the individual smoker. Following consent, baseline assessment, and provider intervention (all done within clinic), follow-up assessment (coordinated centrally through our study team) will continue at +1, +3, and +6 months. The primary outcome will be 7-day point prevalence abstinence at 6-month follow-up, though we track a number of other outcomes as well. A recent trial of comparative effectiveness for single/combined pharmacotherapy (79) provided strong framework for our decisions. As a comparative effectiveness study, our guiding philosophy is to optimize ecological (i.e., external) validity, while at the same time maintaining basic standards of scientific rigor.

